3. STUDY PLAN

3.1 Overall Design

This Phase 2 study will be a an interventional, open-label, single arm trial where each patient is his/her own “intrapatient” control usin two Grou s. All patients will receive a single mg/kg dose of pegasitacianine prior to standard of care surgery.

Patients enrolled in Group 1 of the study will have a biopsy confirmed diagnosis of non-mucinous peritoneal carcinomatosis, defined as less than, or equal to 50% mucin in the sample, with a suspected Peritoneal Carcinomatosis Index (PCI) greater than or equal to . Group 2 of the study will include patients with a suspected PCI greater than or equal to and a biopsy confirmed diagnosis of mucinous peritoneal carcinomatosis, defined as > 50% mucin in the sample. A total of approximately 60 patients will be enrolled across both Groups. Enrollment will be open first to Group 1 with the opportunity to open Group 2 for enrollment following the demonstration of satisfactory pegasitacianine sensitivity and specificity values of 70% or greater in Group 1.

In both Groups 1 and 2, the surgeon will perform their SOC resection of visible metastases and image each resected specimen, and normal specimens on an area of normal tissue using the intraoperative NIR camera; no investigative NIR imaging of the peritoneal cavity will be performed at this time. The SOC specimens are to be resected upon the initiation of surgery and imaged on a section of normal tissue (i.e., mesentery). Specimen names and fluorescence status will be dictated by the surgeon and documented in the Imaging Workbook by the Clinical Research Coordinator.

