6.3 Surgery and Follow-up Visits (Group 1 and 2)

Procedures at the time of cytoreductive surgery

The following procedures will be performed on the day of surgery:

- Record the patient's vital signs (only if they were abnormal at dosing)

- Obtain blood for routine laboratory tests
- Record all medications being taken, including prescription, over-the-counter, and herbal medications
- Discuss with the patient any new or unexpected changes they are feeling
- Record any AEs

Once the patient is under anesthesia, some procedures will occur that would not normally be part of surgery if the patient were not in this study. The SOC surgical procedures will be allowed to continue with the addition of the steps listed below.

- During SOC resection, the surgeon will select up to 15 (10 suspected tumor and 5 normal) specimens that will be imaged using the intraoperative camera on a section of normal tissue following excision (*Note: NIR camera should not be used to examine the peritoneal cavity at this time*)
 - A total of up to 15 specimens are to be imaged: 5 representative normal pieces of tissue and 10 individual suspected tumor specimens
 - The SOC specimens are to be resected upon the initiation of surgery and imaged on a section of normal tissue (i.e., mesentery) immediately following the collection of all SOC samples
 - The width of the camera's field of view is to be confined to a distance of 10 cm. A surgical ruler is to be placed in frame to control the width of the field of view
 - Note: while there are no specimen size stipulations provided in this protocol, the samples must be able to be imaged within the 10 cm wide imaging window.
 - For samples with multiple nodules, individual nodules should be dissected away from the bulk sample and imaged individually as single specimens.
 - Representative normal sections of tissue should be imaged in an analogous manner
- Samples will be imaged using the NIR camera and fluorescence status and specimen name will be dictated by the surgeon for documentation by the clinical research coordinator in the provided Imaging Workbook
- Once the SOC resection is complete, the surgeon will dictate their completeness of cytoreduction score to the clinical research coordinator for documentation prior to examining the peritoneal cavity with the intraoperative NIR camera in search of additional fluorescent metastatic disease that was missed during SOC

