 - The peritoneal cavity will be evaluated using a manner similar to that used for

the calculation of the Peritoneal Carcinomatosis Index. Specifically, the peritoneal cavity will be examined in a methodical manner using the 13 described regions used for calculating the PCI score

- If additional fluorescent areas are to be collected, an image of the additional fluorescent lesion(s) is to be captured prior to excision from the patient
 - The camera should be held 15 cm away from the area of tissue to be excised. The camera's distance can be measured using an available surgical ruler
- Additional fluorescent lesions will then be removed and imaged on a section of normal tissue in a manner analogous to the SOC specimens with the surgeon dictating fluorescence status and specimen name to the clinical research coordinator for documentation
 - The width of the camera's field of view is to be confined to a distance of 10 cm. A surgical ruler is to be placed in frame to control the width of the field of view

Day 10 (± 5 days) or Day of Discharge (Whichever event occurs first)

- Record the patient's vital signs
- Perform 12-lead ECG to monitor heart activity
- Perform a physical examination
- Obtain blood samples for routine laboratory tests
- Record all medications being taken, including prescription, over-the-counter, and herbal medications
- Discuss any new or unexpected changes they are feeling.
- Record any AEs

Day 28 (± 5 days) after dosing

- Obtain blood samples for routine laboratory tests, including a pregnancy test for females who are capable of becoming pregnant
- Record all medications they are taking, including prescription, over-the-counter, and herbal medications
- Discuss new or unexpected changes they are feeling
- Record the patient's vital signs

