9.4 Imaging Analysis

Diagnostic performance of pgsitacianine will be assessed at the level of the specimen by calculating the *ex situ* sensitivity, specificity, PPV, and NPV of pgsitacianine in detecting tumor containing tissue. The *ex situ* fluorescence status of collected SOC and pgsitacianine guided specimens will be compared to the histological analyses of the collected specimens (which is used to determine each sample's status as true/false positive/negative). For determining these operating characteristics, consider the following definitions:

- False positive is defined as “fluorescence was observed on the specimen but the specimen was not found to have tumor via histological analysis”.
- False negative is defined as “no fluorescence was observed on the specimen but the specimen was found to have tumor via histological analysis”.

- True positive is defined as “fluorescence was observed on the specimen and the specimen was found to have tumor via histological analysis”.
- True negative is defined as “no fluorescence was observed on the specimen and the specimen was found not to have tumor via histological analysis”.

The number of specimens in each category (each combination of true/false positive/negative), along with the true/false positive/negative rates (and corresponding exact two-sided 95% confidence intervals) will be reported. These rates will be used to determine pegsitacianine’s tumor detection sensitivity, specificity, PPV, and NPV using the following equations:

$$\text{Sensitivity} = \frac{\text{\# of True Positive Specimens}}{\text{\# of True Positive + False Negative Specimens}}$$

$$\text{Specificity} = \frac{\text{\# of True Negative Specimens}}{\text{\# of True Negative Specimens + \# of False Positive Specimens}}$$

$$\text{PPV} = \frac{\text{\# of True Positive Specimens}}{\text{\# of True Positive + False Positive Specimens}}$$

$$\text{NPV} = \frac{\text{\# of True Negative Specimens}}{\text{\# of Tumor Negative + False Negative Specimens}}$$

These rates will be reported along with exact two-sided 95% confidence intervals.

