5.1.2 Diagnostic Imaging Endpoints

Diagnostic performance of pegasitacianine will be assessed by calculating sensitivity, specificity, NPV and PPV of pegasitacianine in detecting tumor containing tissue. The *ex situ* fluorescence status (any fluorescence vs. no fluorescence) of collected SOC and pegasitacianine guided specimens, as well as lymph nodes, will be compared to histological analyses of the collected specimens. Sensitivity and specificity for detecting tumor-containing tissue versus normal tissue

will be evaluated using tissue specimen fluorescence and the corresponding pathological outcomes.

True/false negative/positive definitions are as follows:

- False positive is defined as fluorescence was observed on the sample but the sample was not found to have tumor via pathology.
- False negative is defined as no fluorescence was observed on the sample but the sample was found to have tumor via pathology.
- True positive is defined as fluorescence was observed on the sample and the sample was found to have tumor via pathology
- True negative is defined as no fluorescence was observed on the sample and the sample was found not to have tumor via pathology.

Pegsitacianine sensitivity and PPV will be calculated using the following equations:

$$\text{Sensitivity} = \frac{\# \text{ of True Positive Specimens}}{\# \text{ of True Positive Specimens} + \# \text{ of False Negative Specimens}}$$

$$\text{PPV} = \frac{\# \text{ of True Positive Specimens}}{\# \text{ of True Positive Specimens} + \# \text{ of False Positive Specimens}}$$

Specificity values and negative predictive values (NPV) calculated by the equation below:

$$\text{Specificity} = \frac{\# \text{ of True Negative Specimens}}{\# \text{ of True Negative Specimens} + \# \text{ of False Positive Specimens}}$$

$$\text{NPV} = \frac{\# \text{ of True Negative Specimens}}{\# \text{ of True Negative Specimens} + \# \text{ of False Negative Specimens}}$$

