7.10.2 Secondary Analyses

7.10.2.1 Analysis of Diagnostic Imaging

The positive predictive value, negative predictive value, sensitivity, and specificity (biopsy level) will be calculated and summarized for each Group. The summary will include the true/false negatives/positive rate and number of specimens. Two-sided 95% confidence intervals will be calculated for each rate via Clopper-Pearson method.

A listing by subject and specimen showing the fluorescence status, pathology result, specimen type (SOC vs. fluorescence), suspicious vs. normal, fluorescence in *in situ* and *ex situ*, and fluorescence measures (MFI, SBR or TBR) will be provided.

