7.10.3.3 Adjustment for Clustering

There is potential for within-subject correlation to bias our estimates of pegasitacianine's diagnostic accuracy. To assess this issue, an ROC curve will be constructed from a mixed model that clusters specimens by the subject they originated from. We will compare the AUC of the mixed effects ROC curve to the standard ROC curve to assess if within-subject correlation is causing significant bias in our analyses. If it is determined that significant bias has been introduced, additional analyses on secondary endpoints may be performed to assess the diagnostic accuracy of pegasitacianine.

The confidence intervals for diagnostic accuracy (e.g. the positive predictive value, negative predictive value, sensitivity, specificity, and true/false negative/positive rate) will also be constructed via a cluster-bootstrap to determine confidence intervals that account for the effects of within-subject clustering. Since the number of specimens each subject has is variable, in order to keep the same number of specimens in the bootstrapped sample, we will cluster initially by the number of specimens each subjects has, and then resampling will occur by first choosing a subject within that cluster and then resampling the same number of specimens they originally had.

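### The secondary accuracy table pools standard-of-care specimens with specimens excised because they fluoresced, and the SAP prespecifies no split by source, so pooled specificity and PPV can shift with the number of guided excisions

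*SAP*

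**What the plan says.** SAP 5.1.2 defines one set of true/false positive/negative counts and one formula each for sensitivity, specificity, PPV and NPV. The input is the ex situ status of SOC and guided specimens, and it adds nodes: "guided specimens, as well as lymph nodes, will be compared to histological analyses of the collected specimens". Protocol 9.4 pools SOC and guided tissue in the same way but does not name lymph nodes: "guided specimens will be compared to the histological analyses of the collected specimens".

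The two kinds of specimen are collected differently under Protocol 6.3. During SOC resection the surgeon picks suspected-tumor and normal specimens ("A total of up to 15 specimens are to be imaged": at most 10 suspected and 5 normal) under the instruction that the "NIR camera should not be used to examine the peritoneal cavity at this time". The camera is then used to search the cavity, and "Additional fluorescent lesions will then be removed and imaged on a section of normal tissue".

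SAP 7.10.2.1 summarizes accuracy for each Group. Source and suspicious/normal status ("specimen type (SOC vs. fluorescence), suspicious vs. normal") appear there only as per-specimen listing fields. The other planned accuracy analyses (ROC, mixed-model ROC, cluster bootstrap, camera system; SAP 7.10.3.2 to 7.10.3.4) do not split by source. SAP 7.10.3.5 allows optional post-hoc covariates and does not name source.

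Two other planned summaries bear on the point. SAP 7.9.5 summarizes per patient the numbers of SOC suspicious, SOC normal and additional fluorescent specimens, in the Safety population. SAP 7.10.1.1 gives patient-level proportions for each type of clinically significant event (CSE), including occult disease found by fluorescence.

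**The concern.** Guided specimens are selected on the index test. Any that remain fluorescent ex situ can only be true or false positives and can never add a true negative. Mixed with SOC tissue, they produce a specificity and a PPV that partly reflect how many extra excisions the surgeons made. The same agent, with the same performance on surgeon-selected tissue, could then show different pooled values in two studies.

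The primary CSE analysis is not touched. What is at stake is the use of the estimates: SAP 4 says the sample size serves to inform power calculations for future studies, and a pooled figure does not carry over directly to a study with a different number of guided excisions. The cluster bootstrap in SAP 7.10.3.3 is meant to "determine confidence intervals that account for the effects of within-subject clustering". That deals with correlation between specimens, not with selection on the test result.

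**Working it through.** The documents state no expected accuracy, prevalence or number of guided excisions, so there is no planned figure to reproduce. Protocol 1.2 gives earlier accuracy figures, but for other tumor types, and they are not used here.

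**Inputs per patient.** From Protocol 6.3: the SOC maximum of 15 (10 suspected, 5 normal). From SAP 4: about 60 patients, all taken as evaluable. Assumed: 9 of the 10 suspected specimens contain tumor and all 5 normals are tumor-free, giving nT = 9 tumor and nN = 6 non-tumor SOC specimens; SOC sensitivity Se0 and specificity Sp0 both 0.75; g guided specimens, a fraction t with tumor; rT and rN the ex situ fluorescence rates of tumor and non-tumor guided tissue. Lymph nodes are not modelled because no count is given.

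**Formulas** (SAP 5.1.2 definitions applied to the pooled table):

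- Sensitivity = (nT·Se0 + g·t·rT) / (nT + g·t)
- Specificity = (nN·Sp0 + g(1−t)(1−rN)) / (nN + g(1−t))
- PPV = TP / (TP + FP), with TP = nT·Se0 + g·t·rT and FP = nN(1−Sp0) + g(1−t)·rN

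Each is a weighted average of the SOC and guided values. Specificity falls if rN > 1 − Sp0, is unchanged if they are equal, and rises if rN is lower. PPV moves toward guided PPV from either side.

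**SOC only (g = 0).** TP 6.75, FN 2.25, TN 4.5, FP 1.5. Specificity 4.5/6 = 75.0%; PPV 6.75/8.25 = 81.8%; NPV 4.5/6.75 = 66.7%.

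**Two guided specimens, t = 0.5, all fluorescent ex situ.** One TP and one FP are added. Sensitivity 7.75/10 = 77.5%; specificity 4.5/7 = 64.3%; PPV 7.75/10.25 = 75.6%; NPV unchanged at 66.7%.

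**By number of guided specimens (t = 0.5, rT = rN = 1):**

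| g | Specificity | PPV |
|---|---|---|
| 0 | 75.0% | 81.8% |
| 0.5 | 72.0% | 80.0% |
| 1 | 69.2% | 78.4% |
| 2 | 64.3% | 75.6% |
| 4 | 56.3% | 71.4% |

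**By ex situ rate (g = 2, t = 0.5):**

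| rT / rN | Sensitivity | Specificity |
|---|---|---|
| 1 / 1 | 77.5% | 64.3% |
| 1 / 0.6 | 77.5% | 4.9/7 = 70.0% |
| 1 / 0.25 | 77.5% | 5.25/7 = 75.0% (no change) |
| 0.9 / 0.2 | 76.5% | 5.3/7 = 75.7% (rises) |
| 0.6 / 1 | 73.5% (falls) | 64.3% |

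PPV can also rise: with g = 2, t = 0.75 and rates 1 / 0.4, it is 8.25/9.95 = 82.9%.

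**Other assumptions.** With SOC sensitivity 85%, specificity 80% and 8 tumor and 7 non-tumor SOC specimens, 60 patients give SOC specificity 336/420 = 80.0% and PPV 408/492 = 82.9%. Two guided specimens per patient, half tumor and all fluorescent, give 336/480 = 70.0% and 468/612 = 76.5%. The direction is the same.

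**Precision of a split (first set of assumptions, 60 patients, g = 2, exact 95% intervals ignoring clustering).** SOC specificity 270/360 = 75.0% (70.2 to 79.4); pooled 270/420 = 64.3% (59.5 to 68.9). Sensitivity half-width 3.7 points for SOC against 3.4 pooled. Guided PPV 60/120 = 50.0% (40.7 to 59.3).

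**Are SOC predictive values free of the problem?** No. Among the 10 suspicious specimens alone (9 tumor, 1 non-tumor), PPV is 6.75/7.00 = 96.4% and NPV 0.75/3.00 = 25.0%, against 81.8% and 66.7% once the 5 normals are added. The quota of normal specimens moves PPV by about 15 points; the two guided specimens moved it by about 6.

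**The case against.** The strongest reply is that pooling all collected specimens is the stated design, the estimates are secondary, descriptive and unpowered, and most of what a reader needs is already planned: counts of guided areas, a patient-level yield by CSE type, and a listing with source, suspicious/normal status, both fluorescence readings and pathology. The separate document holding the list of tables (SAP 1) was not available and may contain a split. Much of this stands. The gap is one derived table, and it concerns the SAP and Protocol text only. But none of those outputs is a prespecified accuracy summary by source, and a split made from the listing would be chosen after the results are known.

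It is also fair that SOC predictive values depend on the suspected/normal quota. They are no safer for planning than the pooled ones, so simply replacing pooled by SOC figures would not be a sound remedy.

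A reader might infer that pooling must bias specificity downward. The documents do not support that. Status is scored ex situ, so tissue that glowed in situ may read negative after excision, and no loss rate is given. A fall is plausible given how guided tissue is chosen, but no change or a rise is possible.

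**Conclusion.** The point holds as a gap in the prespecified analysis. Following the SAP as written gives one specificity and one PPV per Group that mix surgeon-selected with test-selected tissue, and both can shift with the number of guided excisions without any change in the agent. The shift is zero for specificity if the two non-tumor ex situ fluorescence rates are equal, and zero for PPV if the two PPVs are equal.

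The size is illustrative only: specificity falls from 75.0% to 64.3% with two guided specimens per patient that all stay fluorescent ex situ, or to 70.0% if 60% of the non-tumor ones do. Accuracy, prevalence, guided count and ex situ rates are all assumed; these are examples, not bounds.

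A reader might also link this to the Protocol's rule of opening Group 2 at sensitivity and specificity of 70% or greater. The Protocol does not say which specimens that rule uses, and SAP 3.1 leaves opening to the sponsor, so an effect of pooling on that decision cannot be shown. That conflict, and the one between the cap of 15 SOC specimens in Protocol 6.3 and the instruction to "image each resected specimen, and normal specimens on an area of normal tissue" in Protocol 3.1 (repeated in SAP 3.1), are separate inconsistencies to be reconciled in their own right. Pooling does not cause them.

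**What to change.** In SAP 7.10.2.1, keep the pooled table and add a prespecified table by source, using the fields already listed there:

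1. For SOC specimens, sensitivity and specificity, plus counts, PPV and NPV shown both for suspicious specimens and for suspicious plus normal. Add a note that SOC PPV and NPV depend on the suspected/normal quota and are not direct planning inputs.
2. For guided specimens, PPV and false positives per patient, in the Efficacy population. Sensitivity and specificity say little here: if every guided specimen stays fluorescent ex situ they are 100% and 0% by construction.
3. Assign each lymph node to SOC or guided by how it was collected. The listing names no node identifier, so a separate node row might need one; assignment by collection route would not.

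State that SOC sensitivity and specificity and guided PPV, not only the pooled values, will be used to plan future studies.

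The cost is one table and no new specimen data. SAP 7.1 allows an update before database lock; the documents do not say whether lock has taken place. The downside is fewer specimens in each part and wider intervals, mainly for guided PPV (about ±9 points in the illustration). SOC-only values do not describe occult residual disease, which is why the pooled table should stay.

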5.1.3 Fluorescence Endpoints

Specimen-to-background (SBR) ratios will also be calculated using white light and NIR images of both SOC and pegsitacianine guided specimens. SBRs will be calculated using *ex situ* images of collected specimens. The equation for calculating SBR is listed below.

$$\text{SBR} = \frac{\text{Mean Fluorescence Intensity (Specimen)}}{\text{Mean Fluorescence Intensity (Normal Tissue)}}$$

Note, Tumor-to-background (TBR) ratios are equivalent to SBR, but only relevant for specimens with tumors.

5.2 Safety Endpoints

- TEAE incidence, severity, and relationship to study drug
- Physical examination results
- Vital signs results
- ECG results
- Clinical laboratory values (CMP, hemoglobin, and CBC with differentials)

6. ANALYSIS POPULATIONS

6.1 The Safety Population

All patients who receive at least one dose (either partial or full) of pegsitacianine.

6.2 The Intent-to-Treat Population

Identical to the Safety Population

6.3 The Efficacy Population

All patients who receive >75% intended dose of pegsitacianine, had a minimum of one (1) image collected during their procedure, and had the opportunity for post-SOC evaluation of the peritoneal cavity.

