9.2 Populations

All subjects who receive any dose of the study drug will be included in the intent to treat population. The efficacy population will consist of all subjects who receive >75% of the intended dose of pegasitacianine, had a minimum of one (1) image collected during their procedure, and had the opportunity for post-SOC exploration of the peritoneal cavity. The safety population will include all subjects who were administered pegasitacianine whether it be a full or partial dose.

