7.4 Handling of Dropouts and Missing, Unused and Spurious Data

All data will be analyzed.

No imputation of missing data will be performed, and analyses will use the observed cases only.

Formal outlier testing will not be performed. Data identified as potential outliers after review will be reviewed to determine whether they are spurious.

Spurious data are data determined to be incorrect upon review of site documents. If data is deemed to be spurious, the spurious data and the reason for it being spurious will be documented by the Sponsor in a Note-to-file. Data identified as spurious will be treated as missing unless they can be definitively corrected. If spurious data is identified, sensitivity analysis may be performed to assess the potential impact of any missing data or outliers on trial results by including the spurious data.

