7.10 Efficacy Endpoint Analyses

Imaging will be assessed on the Efficacy population.

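### Specimen-level accuracy is limited to patients who could have post-SOC exploration, a condition that the ex situ endpoints do not need

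*SAP*

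**What the plan says.** SAP 7.10 sets one population for the whole efficacy section: "Imaging will be assessed on the Efficacy population". SAP 6.3 defines that population by three conditions: more than 75% of the intended dose, at least one image, and that the patient "had the opportunity for post-SOC evaluation of the peritoneal cavity". Protocol 9.2 has the same third condition: "had the opportunity for post-SOC exploration of the peritoneal cavity".

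For the secondary endpoints, SAP 5.1.2 says that the ex situ status "of collected SOC and pegasitacianine guided specimens, as well as lymph nodes, will be compared to histological analyses of the collected specimens". SAP 7.10.2.1 adds: "The positive predictive value, negative predictive value, sensitivity, and specificity (biopsy level) will be calculated and summarized for each Group". It names no population of its own, so the rule in 7.10 governs. Protocol 9.4 describes the same accuracy measures and also names no population. SAP 1 gives the SAP precedence on analysis and reporting.

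On timing, Protocol 6.3 has the SOC specimens taken at the start of surgery and "imaged on a section of normal tissue (i.e., mesentery) immediately following the collection of all SOC samples". The camera is not to be used to examine the cavity at that stage. Protocol 3.1 places exploration at the end of SOC resection.

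**The concern.** The exploration condition is sensible for the primary question, since residual disease cannot be found in a cavity that nobody could examine. It has no bearing on whether a resected SOC specimen has a valid fluorescence status and histology. When the two questions share a population, complete index-reference pairs can be dropped for a reason unrelated to their evaluability. SAP section 7 plans no other accuracy analysis that would bring them back.

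Two things are at stake. First, whether an operation stops before exploration may depend on disease extent, so the accuracy sample could lean towards patients whose surgery could be completed. Second, the specimens concerned are informative ones. Guided specimens are chosen because they fluoresce in situ, so they mainly supply positives. The planned normal samples come only from the SOC step. Specificity, NPV and the false-negative count therefore rest largely on SOC specimens.

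The study's stated purpose is to inform power calculations for later trials (SAP 4). Protocol 3.1 also makes Group 1 sensitivity and specificity of 70% or more the condition for opening Group 2, although SAP 3.1 leaves that to the sponsor's discretion.

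**Working it through.** The plan has no figure of its own to reproduce here. The sample size of about 60 rests on historical experience, and SAP 4 gives no drop-out or non-evaluable rate. The check traces the rule and then sizes its effect under stated assumptions.

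**Tracing the rule for one patient.** The patient receives the full dose, the SOC samples are collected and imaged, and the operation then ends with no opportunity for exploration.
- Ex situ status and pathology are available, so the requirements of SAP 5.1.2 are met.
- The dose and image conditions of SAP 6.3 are met; the post-SOC condition is not.
- Under SAP 7.10 the patient's specimens do not enter 7.10.2.1.
- SAP 7.9.5 still summarises the patient's specimen counts in the Safety population, with a listing.

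**Inputs for size.**
- Planned patients: about 60 (SAP 4).
- SOC specimens per patient: up to 15, made up of 10 suspected tumour and 5 normal (Protocol 6.3).
- Affected patients, *k*: not given; assumed 0 to 9.

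**Formulas.** The maximum SOC total is 60 × 15 = 900. SOC pairs lost are at most 15*k*, a share of 15*k*/900 = *k*/60. The standard-error ratio is √(60/(60 − *k*)). For the exact (Clopper-Pearson) 95% half-widths, the 10 suspected specimens are treated as tumour and the 5 normal ones as tumour-free, with a rate of about 70% (nearest whole count). Sensitivity then uses 10(60 − *k*) specimens and specificity 5(60 − *k*).

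| *k* | SOC pairs lost, at most | Share of SOC maximum | SE ratio | Half-width, sensitivity (points) | Half-width, specificity (points) |
|---|---|---|---|---|---|
| 0 | 0 | 0% | 1.00 | 3.74 | 5.33 |
| 1 | 15 | 1.7% | 1.01 | 3.78 | 5.39 |
| 3 | 45 | 5% | 1.03 | 3.84 | 5.46 |
| 6 | 90 | 10% | 1.05 | 3.95 | 5.63 |
| 9 | 135 | 15% | 1.08 | 4.07 | 5.80 |

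These are upper limits on the loss. If the retained patients contribute *G* guided specimens and lymph nodes, the excluded share falls to 15*k*/(900 + *G*). Incomplete sampling in a stopped operation lowers the numerator too. The half-widths ignore within-patient clustering, so actual uncertainty is larger in every row.

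**Selection.** Suppose the Efficacy population shows 80% sensitivity, the excluded patients' specimens have sensitivity *s* between 60% and 90% (assumed), and each patient contributes equally. The all-patient value is ((60 − *k*) × 80 + *k* × *s*)/60.
- *k* = 3: 79.0% to 80.5%.
- *k* = 6: 78.0% to 81.0%.
- *k* = 9: (51 × 80 + 9 × 60)/60 = 77.0% to (51 × 80 + 9 × 90)/60 = 81.5%.

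The shift can go either way, and nothing in the documents fixes *s*.

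**The case against.** The strongest reply is that this is an edge case. The exclusion criteria already remove disease that the surgeon deems inoperable, so few operations may stop after sampling. Opportunity is undefined and is not the same as exploration having taken place, so some patients who were not explored might still qualify. Because imaging waits until all SOC samples are in hand, an operation that stops very early may yield few or no ex situ calls. The trial is descriptive, these endpoints are secondary, and a single population for all imaging results is a defensible choice. All of this stands. It limits the size of the problem but does not remove the mismatch.

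One further objection also stands and affects the remedy. Unexplored patients contribute no fluorescence-selected specimens. Adding them raises the SOC share of the pooled set, which can move PPV and specificity through specimen mix alone.

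A reader might infer that the SAP contradicts itself, because SAP 7.4 states "All data will be analyzed". It does not. That sentence concerns missing, unused and spurious data and does not override a population named for a particular analysis. A reader might also infer that the specimens vanish from the report, but their counts remain in the Safety-population summaries.

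**Conclusion.** The concern holds as a mismatch between population and endpoint. As written, the plan leaves evaluable SOC specimens out of sensitivity, specificity, PPV and NPV when the patient had no opportunity for exploration, and those endpoints do not need that condition.

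The effect on precision is small. With 0 to 9 of 60 patients affected (assumed), at most 0 to 15% of SOC specimens are lost and standard errors grow by about 0 to 8%, less once guided specimens and lymph nodes are counted. Selection is the more serious issue, but its direction and size are unknown.

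It would be tempting to conclude that a material share of the accuracy data will be lost, or that the estimates will be biased in a known direction. The documents support neither: they give no rate of stopped operations, the number may be zero, and 15 specimens per patient is a ceiling. The case for changing the plan rests on the change being cheap and the condition being irrelevant to these endpoints, not on a demonstrated large effect.

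**What to change.** For SAP 7.10.2 and the specimen-level parts of 7.10.3, define an imaging-evaluable set: patients with more than 75% of the intended dose and at least one specimen that has both an ex situ fluorescence status and a pathology result, whether or not exploration was possible. Report SOC and pegsitacianine-guided specimens separately as well as pooled, so that a change in specimen mix is visible. Show the Efficacy-population result as a sensitivity analysis. Keep the post-SOC condition for the CSE analysis in 7.10.1.

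The cost is one population flag and some extra table rows. SAP 7.1 allows updates before database lock, and the primary analysis is unchanged. Because Protocol 9.2 does not list this set, SAP 8 should record the addition. There are two downsides: patient counts will differ between the primary and secondary tables, and the pooled specimen mix will shift slightly because unexplored patients add no guided specimens.
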